## PROTOCOL SYNOPSIS

**Title:** A PHASE II, OPEN-LABEL SAFETY AND TOLERABILITY STUDY OF A RENAL AUTOLOGOUS CELL THERAPY (REACT) IN PATIENTS WITH TYPE 2 DIABETES AND CHRONIC KIDNEY DISEASE (REGEN-003)

**Therapeutic Product:** REACT is made from expanded autologous selected renal cells (SRC) obtained from each individual subject's kidney biopsy. To manufacture REACT, kidney biopsy tissue from each enrolled subject will be sent to ProKidney, where renal cells will be expanded and SRC selected. SRC will be formulated in a gelatin-based hydrogel at a concentration of  $100 \times 10^6$  cells/mL, packaged in a 10 mL syringe, and shipped to the clinical site for use.

**Study Objectives:**

**Primary Objective:** The primary objective of the study is to assess the safety of REACT injected in one recipient kidney.

- Primary Outcome Measures: procedure and/or product related adverse events (AEs) through 24 months post-injection.

**Secondary Objective:** The secondary objective of the study is to assess the safety and tolerability of REACT administration by assessing renal-specific AEs over a 24-month period following injection.

- Secondary Outcome Measures: renal-specific laboratory assessments through 24 months post-injection.

**Exploratory Objective:** Exploratory objectives of the study are designed to assess the impact of REACT on renal function over a 24-month period following injection and on the Quality of Life.

- Exploratory Outcome Measures: 1) clinical diagnostic and laboratory assessments of renal structure and function (including eGFR, serum creatinine, and proteinuria) to assess changes in the rate of progression of renal disease, 2) patient-reported outcomes from the Kidney Disease Quality of Life (KDQOL) and EQ-5D-5L surveys obtained at baseline (i.e., after randomization, but before REACT injection) through 24 months after the last REACT injection.

**Study Design:** Multi-center, prospective, open-label, single-group study. All subjects will be treated with two REACT injections 6 months (+4 weeks) apart after biopsy.

**Randomization:** Open-label, non-randomized.

**Control Group:** Each subject will serve as his or her own control; the patient's previous medical history, which must include a minimum 6-month period of observation of renal function, will serve as the control for rate of progression of renal insufficiency.

**Sample Size:** Up to 10 patients will be treated with REACT. As this is a Phase II safety study, robust statistical analysis will not be performed. Therefore, the sample size proposed for this study is a size typical for in Phase 1 studies, allowing for identification of safety outcomes in a limited population.

**Study Population:** Male or female patients 30 to 65 years of age with CKD and eGFR between 14 and 20 mL/min/1.73m^2. Patients should have sufficient historical clinical data to determine their individual rate of CKD disease progression.

**Inclusion Criteria:** Unless otherwise noted, subjects must satisfy each inclusion criterion to participate in the study. Inclusion criteria will be assessed at the Screening Visit, prior to renal biopsy, and before each REACT injection unless otherwise specified.

1. The subject is male or female, 30 to 65 years of age on the date of informed consent.
2. The subject has an established diagnosis of T2DM.
3. The subject has an established diagnosis of diabetic nephropathy as the underlying cause of renal disease.
4. The subject has an established diagnosis of CKD not requiring renal dialysis, defined as having an eGFR between 14 and 20 mL/min/1.73m^2 inclusive at the Screening Visit and prior to REACT injection.
5. The subject has blood pressure less than 150/90 at the Screening Visit, prior to renal biopsy, and prior to REACT injection(s). At the time of the biopsy and injections, the subject's BP should not be significantly below the previously recorded stable pressure.
6. The subject has stable blood pressure and is maintained on a stable anti-hypertensive medication regimen, if treatment for hypertension is necessary. If treatment includes an angiotensin-converting-enzyme inhibitor (ACEI) or an angiotensin receptor blocker (ARB), that treatment must have been initiated at least 8 weeks prior to renal biopsy. Treatment must be stable during the 6-week period immediately prior to REACT injection. Stable treatment is defined as dose adjustment to no less than one half of the current dosage or to no more than 2 times the current dosage. Dose interruptions up to 7 days due to medical necessity are allowed.
7. A minimum of 3 measurements of eGFR or sCr should be obtained at least 3 months apart prior to the Screening Visit or within the previous 24 months to define the rate of progression of CKD. The subject should have adequate, historical clinical data to provide a reasonable estimate of the rate of progression of CKD. The Medical Monitor may be consulted to ensure there is sufficient data.
8. The subject is willing and able to refrain from NSAID consumption (including aspirin) as well as clopidogrel, prasugrel, or other platelet inhibitors during the period beginning 7 days before through 7 days after both the renal biopsy and REACT injection(s).
9. The subject is willing and able to refrain from consumption of fish oil and platelet aggregation inhibitors, such as dipyridamole (i.e., Persantine®), during the period beginning 7 days before through 7 days after both the renal biopsy and REACT injection(s).
10. The subject is willing and able to cooperate with all aspects of the protocol.
11. The subject is willing and able to provide signed informed consent.

**Exclusion Criteria:** Subjects who satisfy any exclusion criterion listed below are not eligible to participate in the study. Exclusion criteria will be assessed at the Screening Visit, before renal biopsy, and before each REACT injection unless otherwise noted.

1. The subject has a history of type 1 diabetes mellitus.
2. The subject has a history of renal transplantation.
3. The subject has a serum HbA1c level greater than 10% at the Screening Visit.

4. The subject has uncontrolled diabetes (defined as metabolically unstable by the Investigator).
5. The subject has hemoglobin levels less than 9 g/dL prior to each REACT injection.
6. The subject has abnormal coagulation status as measured by activated partial thromboplastin time (APTT), prothrombin time international normalized ratio (PT INR), and/or platelet count at the Screening Visit.
7. The subject has a bleeding disorder(s) or is taking anticoagulants, such as Coumadin® (warfarin) or direct thrombin inhibitors that, in the judgment of the Investigator, would interfere with the performance of study procedures.
8. The subject has small kidneys (average size less than 9 cm) or has only one kidney, as assessed by ultrasound and/or MRI prior to renal biopsy, unless earlier radiology reports (generated within 1 year of the Screening Visit) are made available to confirm kidney size and number.
9. The subject has a known allergy or contraindication(s), or has experienced severe systemic reaction(s) to kanamycin or structurally similar aminoglycoside antibiotic(s).
10. The subject has a history of anaphylactic or severe systemic reaction(s) or contraindication(s) to human blood products or materials of animal origin (e.g., bovine, porcine).
11. The subject is not a good candidate to undergo percutaneous REACT injection, in the judgment of the surgeon or physician who will perform the procedure. This includes individuals who are morbidly obese (defined as BMI greater than 45 kg/m^2), have excessive fat surrounding the kidney, or who are otherwise at excessive risk for serious complications.
12. The subject has a history of severe systemic reaction(s) or any contraindication to local anesthetics or sedatives.
13. The subject has a clinically significant infection requiring parenteral antibiotics within 6 weeks of REACT injection.
14. The subject has acute kidney injury or has experienced a rapid decline in renal function during the last 3 months prior to REACT injection.
15. The subject has any of the following conditions prior to REACT injection: renal tumors, polycystic kidney disease, anatomic abnormalities that would interfere with the REACT injection procedure or evidence of a urinary tract infection.  
*Note:* anatomic abnormalities are not exclusionary if the kidney remains accessible and meets the criteria to receive the REACT injection.
16. The subject has incapacitating cardiac and/or pulmonary disorders.
17. The subject has a history of cancer within the past 3 years (excluding non-melanoma skin cancer and carcinoma in situ of the cervix).
18. The subject has clinically significant hepatic disease (ALT or AST greater than 3 times the upper limit of normal) as assessed at the Screening Visit.
19. The subject is positive for active infection with Hepatitis B Virus (HBV), or Hepatitis C Virus (HCV), and/or Human Immunodeficiency Virus (HIV) as assessed at the Screening Visit.
20. The subject has a history of active tuberculosis (TB) requiring treatment within the past 3 years.

21. The subject is immunocompromised or is receiving immunosuppressive agents, including individuals treated for chronic glomerulonephritis within 3 months of REACT injection.  
*Note:* inhaled corticosteroids and chronic low-dose corticosteroids (less than or equal to 7.5 mg per day) are permitted as are brief pulsed corticosteroids for intermittent symptoms (e.g., asthma).

22. The subject has a life expectancy less than 2 years.

23. The female subject is pregnant, lactating (breast feeding), or planning a pregnancy during the course of the study. Or, the female subject is of child-bearing potential and is not using a highly effective method(s) of birth control, including sexual abstinence. Or, the female subject is unwilling to continue using a highly effective method of birth control throughout the duration of the study.  
*Note:* A highly effective method of birth control is defined as one that results in a low failure rate (i.e., less than one percent per year) when used consistently and correctly, such as implants, injectables, combined oral contraceptives, some intrauterine devices (IUDs), sexual abstinence, or a vasectomized partner.

24. The subject has a history of active alcohol and/or drug abuse that, in the judgment of the Investigator, would impair the subject's ability to comply with the protocol.

25. The subject's health status would, in the judgment of the Investigator, be jeopardized by participating in the study.

26. The subject has used an investigational product within 3 months prior to REACT injection without receiving written consent from the Medical Monitor.

**Number of Sites:** Up to 10 clinical centers will be included in the study.

**Study Duration:** treatment to begin as soon as the REACT product is made available and assuming a one-month interval prior to receiving the first REACT injection, and assuming a 6-month interval before receiving the second injection, plus a 24 month follow up period after the final injection, the duration of treatment would be:

- 31 months for a series of 2 REACT injections

**Study Enrollment:** up to 10 subjects will be enrolled into the study. Patients who complete screening procedures satisfying all I/E criteria will be enrolled into the study immediately prior to the biopsy. Patients who do not meet all criteria before the biopsy is taken will be considered screen failures. Patients who have a biopsy but are not injected for whatever reason will be discontinued from the study and may be replaced. Once a patient has been injected, the patient will have completed treatment and every effort should be made to ensure the patient completes all follow-up visits.

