## 2. PHASE II TRIAL OBJECTIVES AND PURPOSE

ProKidney is currently developing a regenerative cell-based product, Renal Autologous Cell Therapy (REACT), with the aim of improving renal function in subjects who have CKD and T2DM. Therapeutic intervention with REACT is intended to delay the need for renal replacement therapy (dialysis or transplant) which, based on the current standard-of-care, is inevitable for patients with end-stage CKD. The purpose of the present study is to compare the safety and efficacy of up to 2 injections of REACT given 6 months (+4 weeks) apart (maximum). Each subject's annual rate of renal decline, based on adequate historical clinical data from 24 months prior to the Screening Visit, will serve as a comparator to monitor the rate of progression of renal insufficiency.

We propose that REACT treatment will reduce the rate (slope) of eGFR decline and improve renal function over the 24-month period following the last REACT injection.

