6.3.4 Rate of Progression of Renal Disease

Using the IAS, the rate of progression of renal disease will be assessed graphically for eGFR as estimated by the 2009 CKD-EPI serum creatinine equation, serum creatinine, and 24 hour urine albumin, and 24 hour urine protein. For each subject a plot of the lab result versus time (in study days) will be displayed, showing vertical lines at biopsy date, 1st and 2nd injection, and the initiation of dialysis, if it is administered. Additionally, for eGFR, the rate of progression of renal disease will be assessed by estimating the annualized eGFR slope over time for each subject. Each subject will serve as his or her own control. The subject's previous medical history, which must include a minimum of 6 months of observation of renal function, will serve as the control for rate of progression of renal insufficiency. The historical eGFR measurements as well as all on study measurements taken prior to the first REACT injection will constitute the pre-injection period for this analysis.

The annualized rate of eGFR decline for the pre-injection, post-second injection, and post-injection periods will be estimated separately by linear mixed effects models. That is, separate models will be fit for each of the specific time periods: pre-injection, post-second injection, and post-injection periods. Each subject with a minimum of 3 observations during the period of interest will be modeled. The model will include unscheduled visits, and only the last measurement if there was a re-test on the same day.

For the pre-injection period, the linear mixed effects model will include eGFR as the dependent variable, and time (in years, derived as study day/365) as the independent variable. To account for between-subject variability in eGFR trajectories, random slopes and intercepts will be included. An unstructured covariance matrix will be used for the model. If the model cannot be fit with the unstructured covariance matrix, the following structure will be tried in the order listed below (decreasing number of parameters) until the one of them fit the model:

1. First-order autoregressive moving average (ARMA(1,1))
2. First-order autoregressive (AR(1))
3. Compound symmetry (CS)
4. Variance Components (VC)

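### The own-control comparison rests on absolute eGFR slopes alone; if loss is roughly proportional, the slope flattens after injection with no treatment effect, so a log-scale sensitivity analysis is needed

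*Protocol*

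**What the plan says.** The Protocol Synopsis (Control Group) makes each subject his or her own control: the subject's past record "will serve as the control for rate of progression of renal insufficiency". The same paragraph sets a lower limit on that history, "which must include a minimum 6-month period of observation of renal function". Protocol Section 2 bases the comparator on a longer look-back, "based on adequate historical clinical data from 24 months prior to the Screening Visit", and states the expectation that "REACT treatment will reduce the rate (slope) of eGFR decline and improve renal function". Inclusion criterion 4 requires "having an eGFR between 14 and 20" (mL/min/1.73m2), at Screening and again before injection.

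SAP 6.3.4 defines the control data: "The historical eGFR measurements as well as all on study measurements taken prior to the first REACT injection will constitute the pre-injection period". The rates for the pre-injection, post-second injection and post-injection periods "will be estimated separately by linear mixed effects models". The outcome in every model is untransformed eGFR (2009 creatinine equation), linear in time, with random intercepts and slopes. The two post-injection models add baseline eGFR as a covariate; the pre-injection model does not. For each period the table gives the number of subjects, the slope and its standard error. Each subject's eGFR is also plotted against study day, with lines marking biopsy, injections and dialysis. Neither document plans a log-scale slope, a percent change per year or any other relative rate.

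**The concern.** The control and treated periods cover different parts of the eGFR range. In a parallel-group trial, curvature in the natural course would affect both arms alike and largely cancel. Here no concurrent arm exists, so any curvature goes straight into the before-after comparison.

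Under proportional loss, a subject losing a fixed fraction each year loses fewer mL/min/1.73m2 per year as eGFR falls. The later line is then flatter than the earlier one, which is the direction that Protocol Section 2 anticipates. The baseline-eGFR covariate does not correct this. It enters only the post-injection models, as an adjustment for level, and does not put slopes from separately fitted periods on a common scale. Choosing more recent history reduces the problem but does not remove it.

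At stake is how the own-control slope table is read. It is the plan's only numerical estimate of rate before against rate after.

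**Working it through.** The plan states no expected slope, effect size or power, so it has no figure to reproduce. The check asks what the planned slopes show when REACT does nothing.

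**Inputs from the documents.** Entry eGFR 14-20; history from a 6-month minimum up to 24 months; second injection about 6 months after the first; follow-up for 24 months after the second; visit months as in Protocol Section 6.5.

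**Assumptions.** eGFR 17 (midpoint of 14-20) at Screening, with Screening 3 months before the first injection; quarterly history; two further on-study values, 1 and 0.4 months before injection; annual proportional loss r from 5% to 30%; no measurement error.

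**Formulas.** With t in years from first injection, eGFR(t) = 17 × (1 − r)^(t + 0.25). The slope b in each period is the least-squares slope of eGFR on t. Apparent slowing = 1 − b(post) / b(pre).

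Slopes are in mL/min/1.73m2 per year; percentages are from unrounded slopes.

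| Loss per year | History | Pre | Post-injection | Post-second | Apparent slowing (post / post-second) |
|---|---|---|---|---|---|
| 5% | 6 mo | -0.88 | -0.81 | -0.80 | 8% / 9% |
| 5% | 24 mo | -0.91 | -0.81 | -0.80 | 11% / 12% |
| 10% | 6 mo | -1.82 | -1.54 | -1.50 | 15% / 17% |
| 10% | 24 mo | -1.96 | -1.54 | -1.50 | 21% / 23% |
| 20% | 6 mo | -3.91 | -2.76 | -2.63 | 29% / 33% |
| 20% | 24 mo | -4.61 | -2.76 | -2.63 | 40% / 43% |
| 30% | 6 mo | -6.38 | -3.69 | -3.39 | 42% / 47% |
| 30% | 24 mo | -8.34 | -3.69 | -3.39 | 56% / 59% |

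Worked row, 20% loss and 24 months of history: 1 − 2.76/4.61 = 40%, a gap of 4.61 − 2.76 = 1.85. Mean eGFR is 20.5 before the first injection and 12.2 after the second.

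**Starting level.** Another starting value multiplies every slope by the same constant, so the percentages do not change. With 17 at first injection instead of Screening, both slopes are divided by 0.8^0.25 = 0.946, giving -4.87 and -2.92, again 40%.

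**Shape.** With a straight-line course of -2 or -4 per year, pre and post slopes are equal and the artefact is 0.

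**Log scale.** On log(eGFR) the slope is ln(1 − r) in every period, for example ln(0.8) = -0.223 per year, so apparent slowing is 0%.

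**Mixed-model check.** In each scenario 150 trials of 10 subjects were simulated with no treatment effect: entry eGFR uniform on 14-20, between-subject SD of loss 8 percentage points, measurement CV 6%, 24 months of history (all assumed). Random intercept and slope models were fitted, with baseline eGFR in the post-injection models.

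| Mean loss per year | Linear slowing (post / post-second) | Same, values below eGFR 8 dropped |
|---|---|---|
| 10% | 31% / 34% | 32% / 34% |
| 20% | 46% / 50% | 44% / 48% |
| 30% | 60% / 63% | 54% / 60% |

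Dropping low values stands in for the SAP's removal of measurements after dialysis starts. The artefact persists with the covariate in the model. On the log scale, apparent slowing was -1% to 1% with all values kept and 0% to 6% with the low values dropped.

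**The case against.** **The premise is assumed.** Nothing in the documents says that loss is a constant percentage per year, and Protocol Section 1.1.2 describes rising blood pressure aggravating the disease, which could point towards acceleration. The by-subject Phase 1 eGFR results listed for Protocol Section 1.6.3 were not in the text reviewed and could not be used to judge the shape. This stands: the artefact is conditional, and so is its sign.

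**The size may be small.** Inclusion criterion 7 sets no minimum rate of decline, so stable subjects qualify. At 5% per year with 24 months of history the gap is only 0.91 − 0.81 = 0.10. At the other end, a subject at 17 at first injection who loses 30% per year reaches 17 × 0.7^(6.5/12) = 14.0 at 6.5 months, the lower eligibility limit for a second injection. Exclusion criterion 14 also removes recent rapid decline. The lower and middle rows are therefore the more relevant ones.

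**Other displays exist.** A reader might infer that nothing in the plan could reveal the artefact. The documents do not support that. With at most 10 subjects, the individual plots may show smooth flattening unrelated to the injection dates. Treated and untreated kidneys are also compared concurrently by ultrasound and scintigraphy (SAP 6.3.2 and 6.3.3). None of these, however, gives a relative rate of eGFR loss.

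**No claim is tested.** The slopes stand side by side without a difference, ratio, test or success rule, and the endpoint is exploratory. This stands and limits the harm to interpretation.

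**The log scale is not neutral.** Take a linear course of -4 per year, eGFR 17 at first injection, 24 months of history and a real 30% slowing to 4 × 0.7 = 2.8 per year. The log slope moves from about -0.19 to -0.21 per year, an apparent worsening of about 10%. A rule requiring slowing on both scales could therefore hide a real effect.

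**Conclusion.** The point holds as a conditional weakness of an exploratory analysis. If loss is roughly proportional, the planned absolute slopes show a slowing of about 8-11% at 5% loss per year, 15-21% at 10%, 29-40% at 20% and 42-56% at 30% with no treatment effect. These ranges compare the pre-injection and post-injection periods with 6 to 24 months of history, at the scheduled visits. The post-second injection figures are slightly larger. The rates of loss, and proportionality itself, are assumptions.

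Two stronger readings are tempting. One is that the design is known to favour REACT. The documents do not support it, because they do not establish the shape of decline, and an accelerating course would bias the comparison the other way. The other is that a formal before-after inference is invalid. None is planned. What remains is that a flatter slope on the linear scale alone cannot separate a treatment effect from the shape of the natural course.

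**What to change.** In SAP 6.3.4:

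- Add a pre-specified sensitivity analysis that fits the same pre-injection, post-second injection and post-injection models to log(eGFR).
- Tabulate percent change per year, 100 × (exp(slope) − 1), and the mean eGFR in each period beside the planned slopes.
- State that a flatter slope seen only on the linear scale will be reported as dependent on the assumed shape of decline and not, by itself, as evidence of slowing by REACT.
- Do not make agreement on both scales a condition for describing slowing.

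The cost is SAP wording, one repeated set of models on data already collected, and extra rows in an exploratory table. The two scales may disagree; if they do, the report should show both and say so.
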